3 STUDY IMPLEMENTATION

3.1 STUDY DESIGN

This is a phase I/II pilot open-label, trial of off label oral ruxolitinib that will enroll up to 35 patients with smoldering or chronic or biologically indolent lymphomatous or acute subtype ATL.

Each treatment cycle will be 28 days in length and new patients will begin treatment at 30 mg orally twice daily. If this dose is tolerated without exceeding the criteria for maximum tolerated dose (MTD) during the first cycle of treatment, the tolerability of treatment at 40 mg and then 50 mg twice daily will be evaluated. A total of 9 patients will be treated at the MTD or maximum administered dose (MAD) to better evaluate the clinical activity of the augmented dosing regimen. The start of subsequent treatment cycles may be delayed up to 7 days for social reasons or patients' convenience without impacting on a patient's ability to continue protocol treatment.

Patients who begin treatment with the higher dose level will stay local to the NCI Clinical Center for their initial 2 weeks of treatment. These patients will be monitored closely for the first month of treatment for the emergence of AEs. The patients will be seen in the outpatient clinic twice during the first week (day 1 and day 4 or 5) after starting treatment and on day 8 during week 2 for clinical and AE assessment, to have standard chemistry and hematology tests. If a patient appears to be tolerating their first 2 weeks of treatment well (grade 1 and 2 AEs) are considered reliable and have a referring physician willing to perform standard laboratories weekly (days 15 and 22 ± 2 days), they may be eligible to be monitored at home for the 3rd and 4th weeks of their cycle 1 treatment. Patients who have new complaints suggestive of toxicities will be seen as soon as possible for outpatient assessment of their condition. Patients who cannot meet these conditions or where there is concern that DLT will occur will remain near the NCI Clinical Center until completion of their cycle 1 treatment.

3.1.1 Dose Limiting Toxicity

Patients must complete their first cycle of treatment (28 days) without interruption or dose adjustment or DLTs to continue protocol specified treatment.

DLT will be defined as follows:

Any grade 3 or 4 toxicity, if deemed possibly, probably or definitely related to the study drug by

the PI during the first cycle of treatment, **with the following exceptions:**

- Grade 3 anemia without hemolysis
- Grade 3 or 4 granulocytopenia or leukopenia without infection
- Grade 3 thrombocytopenia without bleeding
- Grade 3 or 4 lymphopenia

Patients who tolerate treatment at these higher dose levels without DLTs will continue treatment at their initial dose level for the remainder of their protocol treatment and will not be eligible for further dose escalation. Patients who subsequently develop \geq grade 3 toxicities after the DLT evaluation period will hold their treatment until this toxicity resolves.

The following toxicities will not require discontinuation of study drug, but treatment will be interrupted for a maximum of 10 days until the toxicity has resolved:

- Reversible grade 3 or 4 anemia without hemolysis
- Reversible grade 3 or 4 granulocytopenia or leukopenia without infection
- Reversible grade 3 or 4 thrombocytopenia without bleeding
- Reversible grade 3 or 4 non-hematologic toxicities
- Reversible grade 3 or 4 lymphopenia

These patients will be eligible to resume treatment at their starting dose one time if their AEs resolve within the 10-day treatment break; however, treatment will discontinue for recurrence of AE(s). Patients whose neutropenia does not resolve promptly may receive standard dose G-CSF to speed the recovery, but patients may not receive simultaneous G-CSF and Ruxolitinib.

Patients who have evidence of an ongoing response will continue their treatment in the absence of unacceptable toxicity or disease progression. All treatment cycles will be 28 days in length and patient's response to treatment will be assessed by FACS analysis and/or radiographic assessment of their disease performed after cycles 1, 2 and subsequent even numbered cycles. Patients will continue ruxolitinib until they experience unacceptable side effects, there is worsening of the ATL or a complete response is achieved. Response is defined in the report ⁴ of the 2009 International Consensus Meeting on ATL.

Patients who achieve a complete response will receive an additional 56 days (2 cycles) of treatment beyond the assessment that documented their CR and then stop treatment. These patients will continue to have disease reassessments every 3 months for evidence of relapse after completion of treatment.

3.1.2 Dose Escalation

Dose escalation will proceed in cohorts of 3-6 patients. The MTD is the dose level at which no more than 1 of up to 6 patients experience DLT during the first cycle (28 days) treatment, and the dose below that at which at least 2 (of \leq 6) patients have DLT as a result of the drug. If a patient did not experience DLT and did not finish treatment, he or she will not be evaluable for toxicity and will be replaced in the dose level.

Dose Escalation Schedule	
Dose Level	Dose of Ruxolitinib
Level 1	30 mg PO BID
Level 2	40 mg PO BID
Level 3	50 mg PO BID

Dose escalation will follow the rules outlined in the table below; this study plans to treat 9 patients at the MTD/MAD:

Number of Patients with DLT at a Given Dose Level	Escalation Decision Rule
0 out of 3	Enter up to 3 patients at the next dose level
≥ 2	Dose escalation will be stopped. This dose level will be declared the maximally administered dose (highest dose administered). Up to three (3) additional patients will be entered at the next lowest dose level if only 3 patients were treated previously at that dose.
1 out of 3	Enter up to 3 more patients at this dose level. 
• If 0 of these 3 patients experience DLT, proceed to the next dose level.• If 1 or more of this group suffer DLT, then dose escalation is stopped, and this dose is declared the maximally administered dose. UP to three (3) additional patients will be entered at the next lowest dose level if only 3 patients were treated previously at that dose.
≤ 1 out of 6	This is the MTD and is generally the recommended phase 2 dose. NOTE: If ≤ 1 out of 6 patients with DLT occurs at DL3, the MTD will not have been identified and DL3 will be declared the MAD for further study.

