2.3.1 Treatment Assignment and Randomization/Stratification Procedures

2.3.1.1 Cohorts

Number	Name	Description
1	T-Cell Leukemia patients (CLOSED)	HTLV-associated smoldering, chronic, or clinically indolent T-cell leukemia (ATL) (12 subjects)
2	T-Cell Leukemia patients – Dose Escalation	HTLV-associated smoldering, chronic, or clinically indolent T-cell leukemia (ATL) (up to 20 subjects)
3	T-Cell Leukemia patients – Dose Expansion	HTLV-associated smoldering, chronic, or clinically indolent T-cell leukemia (ATL) (up to 6 subjects)

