3.8.1 Off-Treatment Criteria

- Unacceptable toxicity as defined in Section [3.1.3](#) or [3.3](#)
- Disease progression not responsive to highest dose level that can be safely administered
- Persistent (> 14 days) treatment-related adverse events \geq grade 2
- Investigator discretion
- Positive pregnancy test

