Updated Study Design (Amendment D): Although there were 4 responding patients in the first 12 patient who were treated, the activity was not sustained even in these patients; therefore, we are now changing the treatment regimen to evaluate the activity of augmented dosing (effective with Amendment D). We plan to treat a total of 9 patients at the MTD or MAD and will not proceed with the same original two-stage phase 2 dosing. Patients who discontinue treatment within the first 28 days for reasons other than toxicity will be considered inevaluable. In order to allow for this assessment of patients attempting higher treatment doses, the protocol will require an additional 15-21 patients. Accounting for the previously enrolled 12 subjects, the new design, and to assess up to 9 patients for response at the MTD/MAD level with the new increased dose levels as well as allowing for up to two (2) inevaluable patients: the new accrual ceiling will be set at 35 patients.

The major objective of this study continues to be to determine the antitumor activity of ruxolitinib with regard to response rate and time to progression. Response rate will be based on the number of patients who achieve either a complete or partial response to therapy. Time to progression will be measured from the date of registration until documentation of disease progression..

An exploratory analysis will be performed in the two subgroups of patients defined by the inhibition of their pretreatment *in vitro* ATL cells proliferation by ruxolitinib treatment. The patients will be distinguished on the basis of the results of a 6-day *ex vivo* culture analyses performed on patient peripheral blood mononuclear cells prior to drug administration. One subgroup of patients will be defined as those who fulfill the following criteria: peripheral blood mononuclear cells proliferate *ex vivo* ($\geq 5,000$ CPM/1 μ C) in 6-day culture and their thymidine uptake must be reduced by 40% by the addition of 10 μ M ruxolitinib. The other group of patients would be all the remaining treated patients that do not fulfill these criteria. Since a limited number of patient samples have been assessed to date, it is not clear what percentage of smoldering or chronic stage ATL patients will fulfill the criteria for group 1.

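### Section 3.3 applies hold-and-resume to the events for which Section 3.1.3 ends treatment; a smaller point is that Section 3.1.2 replaces patients whom non-DLT drug toxicity stops in cycle 1

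*Combined protocol and SAP*

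**What the plan says.** **Holding and stopping drug.** Section 3.3 forbids dose changes for individual patients. For toxicities listed in Section 3.1.3 that arise after cycle 1, it holds drug for up to 10 days and then resumes it once at the starting dose. Section 3.1.3 uses its list for the opposite purpose. It ends treatment for related grade 4 infection, febrile neutropenia treated with IV antibiotics, bleeding with thrombocytopenia, sustained organ dysfunction, or clinically significant biochemical abnormalities lasting more than 10 days. Section 3.8.1 cites 3.1.3 (and 3.3) for unacceptable toxicity that takes a patient off treatment. A separate list in 3.1.1 names reversible toxicities that lead to a break of at most 10 days and one restart.

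**Evaluability in the 3+3.** Section 3.1.2 defines the MTD as the level where "no more than 1 of up to 6 patients experience DLT during the first cycle (28 days) treatment". Its rule for anyone who leaves early reads: "did not experience DLT and did not finish treatment, he or she will not be evaluable for toxicity and will be replaced". The substitute enters at the same level. Section 8 says that patients who stop within 28 days "for reasons other than toxicity will be considered inevaluable", without saying evaluable for what; the same paragraph plans "to assess up to 9 patients for response at the MTD/MAD level". Section 3.1.1 adds: "Patients must complete their first cycle of treatment (28 days) without interruption or dose adjustment or DLTs to continue protocol specified treatment".

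**Accrual.** Section 8 allows two inevaluable patients and states that "the new accrual ceiling will be set at 35 patients". The cohort table in 2.3.1.1 gives escalation "up to 20 subjects".

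**The concern.** The first matter is patient safety. Section 3.3 is an operative dosing rule. A clinician who follows its cross-reference is told to hold and restart drug for events that 3.1.3 treats as the end of therapy. The drug is being tested above its standard dose, in patients whose disease already predisposes them to infection.

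The second concerns the MTD, which is part of the primary objective and rests on 3 to 6 evaluable patients per level. A patient whom the drug itself prevents from completing 28 days, without meeting the DLT definition, is informative about tolerability. Section 3.1.2 drops that patient from the count and enrolls another. The escalation table counts only DLTs, and the study stopping rule in 3.1.3 counts only events of grade 4 or greater, so a stop for persistent grade 2 toxicity enters neither formal rule.

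**Working it through.** **1. The hold list: sections side by side**

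| Section | Action | Applies to |
|---|---|---|
| 3.1.1 | Interrupt for at most 10 days, resume once | Reversible grade 3 or 4 cytopenias without complication; reversible grade 3 or 4 non-hematologic toxicities |
| 3.1.3 | Discontinue | Grade 4 infection, febrile neutropenia with IV antibiotics, bleeding with thrombocytopenia, sustained organ dysfunction, prolonged biochemical abnormality |
| 3.3 | Hold up to 10 days, resume once | The 3.1.3 list, by cross-reference |
| 3.8.1 | Off treatment | Unacceptable toxicity as set out in 3.1.3 or 3.3 |

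The terms of 3.3 match 3.1.1, not 3.1.3. Changing the section number is not enough, because a grade 4 infection that resolves fits both the non-hematologic item in 3.1.1 and the 3.1.3 list. An order of precedence is needed.

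**2. Who is replaced despite drug toxicity**

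Related grade 3 or 4 non-hematologic toxicity in cycle 1 is already a DLT. The remaining routes are:
- "Persistent (> 14 days) treatment-related adverse events" of grade 2 or more (3.8.1). To end treatment within a 28-day cycle, the event must begin in about the first 13 days.
- Related biochemical abnormalities lasting more than 10 days (3.1.3) that are not already DLTs.
- Possibly, DLT-exempt cytopenias that interrupt cycle 1. Section 1.6.4 reports grade 4 neutropenia in one of 3 subjects at 50 mg twice daily, but no sentence clearly requires holding drug in cycle 1 for an exempt cytopenia.

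**3. The plan's accrual figure**

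Additional patients: 3+3+9 = 15 to 6+6+9 = 21. Ceiling: 12+21+2 = 35. Both reproduce, leaving 35-12 = 23 places for new patients.

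**4. Chance that a dose level passes**

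A level passes on 0 of 3 DLTs, or on 1 of 3 followed by 0 of 3:

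f(r) = (1-r)^3 + 3r(1-r)^5

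Let d be the DLT rate and t the rate of cycle-1 toxicity stops without DLT. Both are assumptions, since the protocol gives neither. Then r = d if such patients are kept as non-DLT, d/(1-t) if replaced, and d+t if counted as DLTs.

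Example with d = 0.10, t = 0.20:
- Kept: f(0.10) = 0.729 + 0.177 = 0.906
- Replaced: r = 0.10/0.80 = 0.125; f = 0.670 + 0.192 = 0.862
- Counted: r = 0.30; f = 0.343 + 0.151 = 0.494

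| d | t | Kept | Replaced (3.1.2) | Counted as DLT |
|---|---|---|---|---|
| 0.10 | 0.05 | 0.906 | 0.897 | 0.814 |
| 0.10 | 0.10 | 0.906 | 0.887 | 0.709 |
| 0.10 | 0.20 | 0.906 | 0.862 | 0.494 |
| 0.20 | 0.05 | 0.709 | 0.686 | 0.600 |
| 0.20 | 0.10 | 0.709 | 0.660 | 0.494 |
| 0.20 | 0.20 | 0.709 | 0.600 | 0.309 |

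**5. Accrual under replacement**

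Simulation of the 3.1.2 rules used 60,000 trials per setting, d = 0.10 at every level, six evaluable patients completed at the MTD/MAD, then three more to reach nine, with every toxicity stop replaced. For t = 5%, 10%, 20% and 33%:
- Escalation exceeds 20 patients in 0.3%, 2%, 11% and 34% of trials.
- New patients exceed 23 in 0.4%, 3%, 15% and 44%.

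The second line assumes that expansion drop-outs are also replaced, which 3.1.2 does not clearly require.

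**The case against.** On the hold list, the defense is that the intent is recoverable: 3.1.1 holds the matching terms, 3.1.3 and 3.8.1 both end treatment, and 3.3 itself opens by discontinuing patients with late clinically significant toxicity. That makes a wrong section number the likely explanation, and nothing suggests that restarting after a grade 4 infection was intended. The instruction as printed still says otherwise.

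On evaluability, several objections have force. A reader might infer that the count of these patients is left undefined. It is not: 3.1.2 says they are replaced. Nor must the two sections conflict, since 3.1.2 speaks of toxicity and Section 8 can be read as speaking of response. A reader might also infer that replacement makes escalation too easy. That holds only against counting these patients as DLTs; against keeping them as non-DLT, replacement is the stricter rule. Nor are the events hidden: 3.1.3 summarizes AEs for all patients, and 7.4.1 bases escalation decisions on the toxicity data from earlier patients at roughly weekly meetings.

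Large stop rates are also unproven. Section 1.5.2 reports hematologic events leading to discontinuation in under 1% of patients, and Section 1.6.3 reports few side effects at 20 mg, though neither covers 30 to 50 mg.

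What stands is that the formal 3+3 count excludes patients stopped by the drug, and that Section 8 draws the line differently without saying for what purpose.

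**Conclusion.** The 3.3 cross-reference is wrong as written and should be corrected on patient-safety grounds. It has no numeric effect and does not bear on the MTD, because it concerns events after cycle 1.

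The replacement rule is a smaller point about a narrow group. At an assumed d of 10% and t of 5% to 20%, replacement lowers the chance of passing a level by 1 to 4 percentage points against keeping the patients. It raises that chance by 8 to 37 points against counting them as DLTs (0.897-0.814 = 0.083; 0.862-0.494 = 0.368). The direction therefore depends on the comparison, and the documents do not support a claim that the current rule is anti-conservative in general.

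Nor do they support expecting a breach of the 35-patient ceiling: that becomes material only at assumed stop rates of about 20% or more.

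**What to change.** 1. In 3.3, refer to the hold list in 3.1.1. State that the 3.1.3 discontinuation list overrides the 3.1.1 item on reversible grade 3 or 4 non-hematologic toxicities.
2. In 3.1.2, limit replacement to patients who stop during cycle 1 for reasons other than drug toxicity.
3. In 3.1.1 and 3.1.2, count a patient who cannot complete cycle 1 because of drug-related toxicity as having a DLT.
4. In Section 8, state whether inevaluable refers to toxicity or to response.

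This is a wording amendment with no added procedures or planned patients. The downside lies in item 3: by counting these stops, the trial may declare a lower MTD.

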2.3.1.2 Arms

Number	Name	Description
1	Experimental Treatment (CLOSED)	Ruxolitinib 20mg orally twice daily for 28 days. Patient may continue to receive treatment until PD.
2	Experimental Treatment – Dose Escalation	Ruxolitinib 30-50 mg orally twice daily for 28 days to determine the maximum tolerated dose (MTD). Patients may continue to receive treatment until PD or unacceptable toxicity.
3	Experimental Treatment – Dose Expansion	Ruxolitinib at the MTD orally twice daily for 28 days. Patients may continue to receive treatment until PD or unacceptable toxicity.

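### Section 3.1.2 gives the maximum-administered-dose label to both a failed dose and a tolerated one, so the plan contradicts itself on the 9-patient cohort if 30 mg fails

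*Combined protocol and SAP*

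**What the plan says.** Section 3.1.2 schedules three levels: 30, 40 and 50 mg twice daily. An MTD needs no more than 1 of up to 6 patients with DLT. When 2 or more patients at a level have DLT, escalation stops and the table states: "This dose level will be declared the maximally administered dose (highest dose administered". The row for 1 DLT in the first 3 gives the same label if a further DLT follows. Both rows then direct that up to three "additional patients will be entered at the next lowest dose level if only 3 patients were treated previously at that dose".

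The NOTE in the last row covers 50 mg with at most 1 DLT in 6: "the MTD will not have been identified and DL3 will be declared the MAD for further study".

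The response cohort is placed as follows:
- Section 3.1.2: "this study plans to treat 9 patients at the MTD/MAD".
- Section 3.1, and Section 1.6.4 in the same terms: "A total of 9 patients will be treated at the MTD or maximum administered dose (MAD").
- Section 8, updated design: "We plan to treat a total of 9 patients at the MTD or MAD".
- Section 2.3.1.2, Arm 3: "Ruxolitinib at the MTD orally twice daily for 28 days", with no mention of a MAD.

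The only lower dose used in the trial is Arm 1, "Ruxolitinib 20mg orally twice daily for 28 days", which is marked closed and is not in the escalation schedule.

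**The concern.** A single label has two opposite meanings. In the stopping rows it marks a dose that the rule has just rejected. In the NOTE it marks a dose that was tolerated and goes forward. The cohort is then located by that label.

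This does little harm when 40 or 50 mg fails. A tolerated level below normally supplies the MTD, and Arm 3 points to it. At 30 mg nothing lies below. The de-escalation step has no target, no scheduled dose can meet the MTD definition, and MAD is the only term left to locate the cohort.

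Two things depend on how that is resolved: whether anyone else is entered at a dose that failed its own rule, and whether the response cohort, which serves part of the primary objective, opens at all.

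**Working it through.** **1. The plan's own counts.** Section 8 asks for 15 to 21 additional patients and sets a ceiling of 35.
- Minimum: 3 + 3 + 9 = 15. Maximum: 6 + 6 + 9 = 21.
- Ceiling: 12 earlier patients + 21 + 2 inevaluable = 35.

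The figures reproduce. Both ends assume that escalation reaches 50 mg, so neither covers failure at 30 mg.

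**2. The text applied to 2 or more DLTs at 30 mg.**
- Escalation stops, and 30 mg receives the maximum-administered-dose label (3.1.2).
- The next lower level does not exist in the schedule.
- 30 mg cannot be the MTD.
- The cohort goes to the MTD or MAD (1.6.4, 3.1, 3.1.2, 8). In the stopping-row sense that is 30 mg. In the NOTE's sense it is no dose.
- Arm 3 is at the MTD (2.3.1.2), and there is none.
- Section 3.2 ends escalation at an MTD or a tolerated 50 mg. Neither has occurred.

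**3. How likely the branch is.** The documents give no DLT rate at 30 mg, so the rates below are assumptions. With q the rate at 30 mg, failure on first entry has probability

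1 − [(1−q)³ + 3q(1−q)² × (1−q)³].

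- q = 2%: 1 − [0.9412 + 0.0576 × 0.9412] = 0.0046
- q = 5%: 1 − [0.8574 + 0.1354 × 0.8574] = 0.0266
- q = 10%: 1 − [0.7290 + 0.2430 × 0.7290] = 0.0939

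A further route is rejection on refilling: 0 of 3 at 30 mg, then 40 mg is rejected, then 2 or more of the 3 added at 30 mg have DLT. For assumed rates of 5/10/20% at 30/40/50 mg:
- 50 mg rejected, counting its fill to 6: 0.104 + 0.384 × 0.488 + 0.512 × 0.104 = 0.3446
- 40 mg rejected: 0.0939 + 0.729 × 0.3446 × 0.028 = 0.1009
- 30 mg rejected on refilling: 0.8574 × 0.1009 × 0.00725 = 0.0006

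| Assumed DLT rate at 30/40/50 mg | 30 mg fails on first entry | No tolerated dose, any route |
|---|---|---|
| 2/5/10% | 0.0046 | 0.0046 |
| 5/10/20% | 0.0266 | 0.0272 |
| 10/20/30% | 0.0939 | 0.1004 |

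**4. Exposure if the cohort were filled at 30 mg.** Failure among the first 3 leaves 9 − 3 = 6 more patients; failure after 6 leaves 9 − 6 = 3 more. At q = 5% the first-entry probability splits into 0.0073 (at 3) and 0.0193 (at 6), so the smaller number is the likelier.

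**5. The study stopping rule.** Section 3.1.3 requires related toxicity of grade 4 or greater in at least 2 of the first 9 patients. A DLT can be grade 3 (3.1.1). On the DLTs alone, the rule acts only if at least two are grade 4 or greater; two grade 3 DLTs reject 30 mg without triggering it.

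**The case against.** The best defence is that the intended outcome can be inferred. The NOTE is the only place where the abbreviation MAD is tied to a particular dose, and that dose is a tolerated one. Section 3.2 names the same two end points. The stopping rows use a longer phrase without the abbreviation, and the only further entry they allow is at a lower level. Arm 3 is at the MTD. Sections 1.6.4 and 3.1.3 appeal to standard phase I practice, under which failure of the lowest level means that no MTD is found.

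Most of this stands, and it rules out a stronger reading. A reader might infer that the protocol authorises expansion at a failed 30 mg. The documents do not support that: it requires equating two differently worded phrases and setting aside the NOTE, Section 3.2 and the Arm 3 line.

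What the defence does not do is settle the matter. Sections 1.6.4 and 3.1 spell MAD out as the maximum administered dose, which is very close to the stopping rows' phrase. No section takes precedence. The Arm 3 line, read to the letter, would also exclude the tolerated 50 mg that the NOTE sends forward, so it cannot be the controlling text as it stands. The team's weekly dose decisions (7.4.1) and the termination clause (11.1) are discretionary and prescribe no outcome.

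The defence is also right that the branch is unlikely. Section 1.6.3 reports little toxicity in 12 patients at 20 mg. The grade 4 neutropenia seen in 1 of 3 subjects at 50 mg (1.6.4) would not be a DLT here without infection (3.1.1).

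**Conclusion.** The text is wrong as written, at low severity. Section 3.1.2 uses one label in two opposite senses, and if 30 mg fails the plan contradicts itself on whether and where the response cohort is treated. A sensible team would probably not expand at 30 mg, and most of the text leans the same way, but that is inference and not a stated rule.

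The probability of reaching the branch is about 0.5% to 2.7% at assumed 30 mg DLT rates of 2% to 5%, and about 10% at a rate of 10%. These rest on the assumed rates in the table and on independent patients. Someone assuming a 30% DLT rate at 30 mg would get 0.506 on first entry, but nothing in the documents supports a rate that high; the tolerability data favour the low end. The exposure at stake is 3 to 6 patients.

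**What to change.** Change Section 3.1.2:
1. Define MAD as Level 3 when no more than 1 of 6 patients has DLT. In the two stopping rows, replace the maximally-administered-dose label with: *exceeds the MTD; no further patients are entered at this level.*
2. Add: *If Level 1 has 2 or more patients with DLT (at first entry or on refilling), no MTD is declared in the 30-50 mg range and Arm 3 does not open unless the protocol is amended.*

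Sections 1.6.4, 3.1 and 8 can then refer to that definition, and the Arm 3 line can carry the same reference. Whether to amend to 20 mg remains the sponsor's choice.

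The cost is one definition, two reworded rows and one sentence. Sample size, accrual ceiling and assessments do not change.
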